1.4 Tumor Infiltrating Lymphocytes (TILs) with Specificities Against Tumor Associated Antigens

The presumed mechanism of action for pembrolizumab is the removal of T lymphocyte inhibition by masking the PD-1 receptor. Our hypothesis is that the masking of the PD-1 receptor by pembrolizumab results in the activation and proliferation of T lymphocytes with specificities against tumor associated antigens. In untreated lung cancer tumors, we would expect few tumors to have TIL cells with specificities against tumor associated antigens. Based on the response rate to pembrolizumab in advanced lung cancer, we hypothesize that at least 20% of lung cancers would have TIL cells with specificities against tumor associated antigens after pembrolizumab therapy.

Fresh tumor samples will be collected at the time of surgical resection for functional TILs and processed per appendices H or I. For each arm, we will determine the percentage of patients with “detectable”

(percentage of $\geq 0.05\%$ with each value also being at least twice that of the background unstimulated control value) tumor infiltrating lymphocytes (TILs) after protocol treatment. The percentage of patients with TILs for patients who have surgical resection and its exact confidence interval will be estimated.

Tumor tissue will be evaluated to determine what antigens commonly expressed in NSCLC are present. The TILs for that tumor will then be analyzed to determine what tumor antigens the TILs are activated against.

We will evaluate whether presence, quantity or quality of detectable TILs is associated with pathologic response to neoadjuvant therapy. A Fisher exact test will be used to evaluate the association of both the presence and the quality of TILs with pathologic tumor response to neoadjuvant therapy. A Wilcoxon rank sum test will be used to test the association of the quantity of TILs and pathologic response to neoadjuvant therapy.

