4.2 Secondary Objectives

All secondary objectives are considered exploratory in nature, and type I error will not be controlled for multiplicity. P-values for these statistical tests will be provided for descriptive purposes. However, if a statistical test on a secondary outcome is significant at the 2-sided significance level of 0.01, the finding will be considered worthy of future investigation.

- 1) We will estimate the rate of objective response rate for the protocol treatment. The definition of objective response will be measured by RECIST 1.1. The objective response rate (ORR=CR+PR) along with its 95% exact confidence interval will be estimated.
- 2) We will evaluate disease-free survival and patterns of metastases after protocol treatment. Disease-free survival (DFS) is defined as the time from surgical resection to disease recurrence (first disease recurrence or death, whichever comes first) after surgery. The Kaplan-Meier estimator will be used to estimate median DFS and its confidence interval. The frequencies of metastases by site will be tabulated.
- 3) Blood-based biomarkers will be evaluated for changes before and after protocol treatment. The association of the baseline value and the changes of these biomarkers with clinical outcomes, such as objective response, overall survival and disease free survival, will be evaluated using logistics regression and Cox models.
- 4) We will determine the percentage of patients with “detectable” (percentage of $\geq 0.05\%$ with each value also being at least twice that of the background unstimulated control value) tumor infiltrating lymphocytes (TILs) after protocol treatment. The percentage of patients with TILs for patients who have surgical resection and its exact confidence interval will also be estimated.
- 5) We will evaluate whether presence, quantity or quality of detectable TILs is associated with pathologic response to neoadjuvant therapy. A Fisher exact test will be used to evaluate the association of both the

presence and the quality of TILs with pathologic tumor response to neoadjuvant therapy. A Wilcoxon rank sum test will be used to test the association of the quantity of TILs and pathologic response to neoadjuvant therapy.

6) Treatment-related adverse evaluate will be summarized by type and grade.

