17.1.3 Target Lesions

All measurable lesions up to a maximum of two lesions per organ (total 5 maximum target lesions) are considered target lesions. Target lesions should be selected on the basis of their size (lesions with the longest diameter) and their suitability for accurate repeated measurements (either by imaging techniques or clinically). A sum of the longest diameter (LD) for all target lesions will be calculated and reported as the baseline sum LD.

The baseline sum LD will be used as reference by which to characterize the objective tumor response.

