27.0 STATISTICAL METHODS AND ANALYTICAL PLANS

27.1 Statistical Considerations

Sample size justification

Futility Analysis

Futility analysis is often used for assessing clinical efficacy before the trial reaches target accrual and stops the trial early if the therapy clearly performs worse than control. The primary objective of this one-arm phase II trial is not to evaluate the efficacy of pembrolizumab in this population. Since it is unlikely that the therapy will harm the patients, a futility analysis on the percentage of patients with adequate TIL collection is unnecessary.

Evaluation of Investigational Therapy Safety and Feasibility

Analytic methods

Overview

The primary objective of the single arm phase II trial is to determine whether the surgery feasibility rate of neoadjuvant pembrolizumab is not significantly worse than the historical surgical feasibility rate of neoadjuvant chemotherapy. Surgery feasibility rate of a neoadjuvant therapy is the percent of patients who are able to undertake surgery after the neoadjuvant therapy. A total of 30 evaluable patients will be entered to the single arm trial. Taking 15% rate of cancellation and ineligibility into account, the trial will enroll a total of 35 patients and eligible subjects (not screen failures) will be followed for 2 years for both disease recurrence and death. Following that, patients will be followed every 6 months for up to five years.

Primary Objective Sample Size Justification

According to Pisters et al (JCO 2010), approximately 80% of subjects undergo surgical exploration within 42 days of day 1 of the last cycle of standard neoadjuvant chemotherapy. We would like to test the following hypotheses:

$$H_0: p \geq 0.80 \text{ vs. } H_a: p \leq 0.65$$

where p is the true surgery feasibility rates after combined neoadjuvant chemotherapy and pembrolizumab. With 30 evaluable patients receiving protocol treatment, the study has approximately 84.6% power rejecting $H_0: p \geq 0.80$ when $p = 0.65$ at one-sided significance level of 15%.

Adverse event monitoring: In this trial design it is difficult to accurately attribute adverse events to pembrolizumab, surgery, or other causes. Further, the analysis of treatment toxicities as isolated events will not best represent whether or not the combination of pembrolizumab followed by surgery is safe and feasible. Therefore, this safety and feasibility trial will be evaluated by the following criteria:

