- 1) Whether the cumulative percentage of deaths among all treated patients related to any of the study treatments from the first pembrolizumab treatment until 30 days after surgery exceeds 17%.
- 2) If the cumulative percentage of all treated patients deemed unable to go to surgery due to adverse events attributed to neoadjuvant therapy exceeds 20%. The percentage of patients unable to go to surgery after pembrolizumab is a conservative estimate based on data reported for a SWOG trial that studied neoadjuvant chemotherapy in early stage lung cancer (22).

The first 10 treated patients will be evaluated for safety and feasibility. If in the first ten patients the criteria for overall therapy being not safe or feasible is met, accrual to the study will be suspended to allow for investigation. After consideration by the study team and the IRB, a decision will be made as to whether accrual can be resumed, potentially with modifications to entry criteria and/or study conduct. In addition, all toxicity patterns will be monitored by the DCI Safety Oversight Committee.

The trial will be stopped for accrual whenever a total of 35 patients are registered or at least one of the thresholds of the safety and feasibility criteria is exceeded. In the event either of these two thresholds is exceeded, the investigational therapy will be considered “infeasible” in this setting.

Accrual and follow-up

With an expected rate of 2 patients being enrolled each month, the trial will take about 16 months to reach the target accrual. All registered patients will be followed for tumor response, disease free survival and overall survival.

Statistical Analysis Plan

Surgery feasibility rate, the primary endpoint of the trial, will be analyzed using the data from all evaluable patients, who are defined as the patients who meet eligibility criteria and has received at least 1 dose of pembrolizumab. The surgery feasibility rate of neoadjuvant pembrolizumab as well as its confidence interval will be estimated.

Secondary Objectives

All secondary objectives are considered exploratory in nature, and type I error will not be controlled for multiplicity. P-values for these statistical tests will be provided for descriptive purposes. However, if a statistical test on a secondary outcome is significant at the 2-sided significance level of 0.01, the finding will be considered worthy of future investigation.

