- 1) We will estimate the rate of objective response rate for the protocol treatment. The definition of objective response will be measured by RECIST 1.1. The objective response rate (ORR=CR+PR) along with its 95% exact confidence interval will be estimated.

- 2) We will evaluate disease-free survival and patterns of metastases after protocol treatment. Disease-free survival (DFS) is defined as the time from surgical resection to disease recurrence (first disease recurrence or death, whichever comes first) after surgery. The Kaplan-Meier estimator will be used to estimate median DFS and its confidence interval. The frequencies of metastases by site will be tabulated.
- 3) Blood based biomarkers will be evaluated for the changes before and after the protocol treatment. The association of the baseline value and the changes of these biomarkers with clinical outcomes, such as objective response, overall survival and disease free survival, will be evaluated using logistics regression and Cox models.
- 4) We will determine the percentage of patients with “detectable” (percentage of $\geq 0.05\%$ with each value also being at least twice that of the background unstimulated control value) tumor infiltrating lymphocytes (TILs) after protocol treatment. The percentage of patients with TILs for patients who have surgical resection and its exact confidence interval will also be estimated.
- 5) We will evaluate whether presence, quantity or quality of detectable TILs is associated with pathologic response to neoadjuvant therapy. A Fisher exact test will be used to evaluate the association of both the presence and the quality of TILs with pathologic tumor response to neoadjuvant therapy. A Wilcoxon rank sum test will be used to test the association of the quantity of TILs and pathologic response to neoadjuvant therapy.
- 6) Treatment-related adverse events will be summarized by type and grade.
- 7) The proportion of patients with detectable circulating T cells specific against TAA after the protocol treatment will be estimated and its confidence interval will be provided. An exact binominal test will be used to test the increase in the proportion of patients with detectable circulating T cells specific against TAA after the protocol treatment relative to baseline.
- 8) Estimate the rate of pathologic response for neoadjuvant pembrolizumab in early stage NSCLC. The pathologic response rate along with its 95% exact confidence interval will be estimated.

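### Biomarkers are tested against objective response by logistic regression in about 30 patients with a 0.01 flag, but no small-sample method is named; with few responders the default Wald p-value would rarely reach 0.01

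*Combined protocol and SAP*

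**What the plan says.** Section 27.1, secondary item 3, relates the baseline values and changes of blood biomarkers to outcomes "such as objective response, overall survival and disease free survival, will be evaluated using logistics regression and Cox models". Section 4.2, item 3, says the same: "will be evaluated using logistics regression and Cox models". Logistic regression is the method for objective response, which item 1 defines as CR plus PR by RECIST 1.1. Neither section says which test of the coefficient is meant (Wald, likelihood ratio, penalised or exact), or what happens if a marker separates responders from non-responders completely.

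The sample is small: "A total of 30 evaluable patients will be entered to the single arm trial". On status, section 27.1 says "All secondary objectives are considered exploratory in nature, and type I error will not be controlled for multiplicity". It then attaches a consequence to the p-value: a result "significant at the 2-sided significance level of 0.01, the finding will be considered worthy of future investigation".

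No objective response rate is assumed for this trial. The nearest anchor is in section 1.4 (repeated in 5.1.2), and it concerns TILs: "Based on the response rate to pembrolizumab in advanced lung cancer, we hypothesize that at least 20% of lung cancers would have TIL cells".

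Tumour size is also recorded on a continuous scale. Measurable disease is an entry criterion (6.2), re-evaluation follows neoadjuvant treatment (17.1), and section 17.1.3 states that "The baseline sum LD will be used as reference by which to characterize the objective tumor response".

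**The concern.** Maximum-likelihood logistic regression relies on large-sample theory in the number of responders and of non-responders, whichever is smaller. With about six responders the estimated log odds ratio is biased away from zero and its standard error grows along with the estimate. The Wald ratio of the two can therefore stay small even when the groups are clearly different. With complete separation the estimate is infinite and the Wald p-value is meaningless.

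At stake is the usefulness of the 0.01 flag, which is the plan's only stated rule for sorting marker leads. If the flag is read from the default Wald column, a real association with objective response can be missed because of the test chosen, and the miss may be misread as no association. The primary endpoint is not affected.

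**Working it through.** **The plan's own figure.** No power or precision is given for item 3. The only power figure is 84.6% for surgical feasibility. It reproduces as Φ(0.15/√(0.80×0.20/30) − 1.036) = Φ(2.054 − 1.036) = 84.6%, but has no bearing here.

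**Inputs**
- From section 27.1: N = 30; two-sided 0.01, so critical |z| = 2.576.
- Assumed: response rate 20%, so 0.20 × 30 = 6 responders; range 10% to 40% (3 to 12).
- Assumed: marker strength. The documents give none. Range used: correlation ρ = 0.5 to 0.8 between marker and tumour change.

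**Hand check: binary marker, 6 responders, 24 non-responders.** With a of 6 and b of 24 marker-positive, z = ln[a(24−b)/((6−a)b)] / √(1/a + 1/(6−a) + 1/b + 1/(24−b)).
- 5/6 against 1/24: ln(115) = 4.745, SE = √(0.2+1+1+0.0435) = 1.498, z = 3.17. This is the largest finite value.
- 5/6 against 4/24: ln(25) = 3.219, SE = √(0.2+1+0.25+0.05) = 1.225, z = 2.63, just past 2.576.
- 5/6 against 5/24: ln(19) = 2.944, SE = √(0.2+1+0.2+0.0526) = 1.205, z = 2.44, a miss.
- 6/6 against 1/24, a stronger split than any above: the estimate is infinite and Wald gives no usable p-value. The exact probability that all six responders fall among the seven marker-positive patients is C(7,6)/C(30,6) = 7/593,775 ≈ 0.00001.

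**Simulation: continuous marker.** Marker and latent tumour change are bivariate normal with correlation ρ. A patient responds if tumour change falls in the best fraction π. Tests at two-sided 0.01:
- Wald: β̂/SE.
- Likelihood ratio: 2[ℓ(β̂) − ℓ(0)] against χ² with 1 df.
- Firth: the same ratio with ℓ*(β) = ℓ(β) + ½ log|I(β)|.
- Exact Mann-Whitney (Wilcoxon rank-sum).

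Rejection rates, 2,000 to 4,000 trials per cell:

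| Response rate | Test | ρ = 0 | 0.5 | 0.7 | 0.8 |
|---|---|---|---|---|---|
| 10% | Wald | 0.0% | 0.2% | 0.6% | 0.7% |
| 10% | Likelihood ratio | 2.6% | 20% | 48% | 65% |
| 10% | Exact rank-sum | 0.7% | 11% | 33% | 48% |
| 20% | Wald | 0.0% | 2.4% | 7.8% | 9.7% |
| 20% | Likelihood ratio | 1.8% | 28% | 66% | 85% |
| 20% | Exact rank-sum | 1.1% | 21% | 56% | 76% |
| 30% | Wald | 0.1% | 7.2% | 23% | 30% |
| 30% | Exact rank-sum | 0.9% | 28% | 70% | 89% |
| 40% | Wald | 0.2% | 11% | 36% | 49% |
| 40% | Exact rank-sum | 0.5% | 32% | 74% | 93% |

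Firth, run separately at 20%: 0.9% at ρ = 0, then 23%, 58% and 77%. Wald in that run gave 0.0%, then 2.5%, 8.6% and 8.1%. At a 30% response rate Firth gave 29%, 72% and 88%.

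**Exactly 6 responders, normal marker shifted by 0.8, 1.0, 1.5 or 2.0 SD.** Wald 0.3%, 0.9%, 4.0%, 7.7%; exact rank-sum 15%, 25%, 63%, 89%. A check of Wald at 1.5 SD with a standard package gave 3.3%. Complete separation occurred in 1.2% of trials at 1.5 SD and 6.6% at 2.0 SD.

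**The case against.** **The plan does not name Wald.** This stands. The defect is that the test is left open, not that logistic regression was chosen. An ordinary likelihood-ratio test of the same model recovers most of the power, though it runs somewhat liberal (1.8% at a 20% response rate, 2.6% at 10%, against 1%).

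**Six responders is not a document figure.** This also stands. The 20% is a hypothesis about TILs, stated as a minimum and tied to advanced disease. At 30% to 40% responders Wald power is low rather than negligible. The order of Wald against the small-sample tests does not change over the range.

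**The analyses are exploratory.** True, so the cost is lost information. A reader might infer that the whole marker objective would come back empty. The documents do not support that. Item 3 also uses DFS and OS, items 5 and 9 already use Fisher and Wilcoxon tests against pathologic response, and sections 1.5 and 5.1.3 plan plots and descriptive summaries of blood analytes.

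**Why not make percent change in tumour size the main analysis?** Under the model above, Spearman correlation with tumour change has 53% to 99% power at ρ = 0.5 to 0.8, which is tempting. But that model makes response a cut of the same noise-free variable, so the continuous measure wins by construction. If the marker only separates responders from non-responders and is unrelated to size change within each group, Spearman falls to 19% to 35% where Firth has 64% to 91%. Sections 15.1 and 17.3.1 warn of inflammatory enlargement, and change in the target-lesion sum ignores new and non-target lesions. It would also change the outcome that item 3 names.

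**Are the Cox models equally at risk?** A reader might extend the point to them. No calculation supports it, and section 1.1 cites recurrence of 35% to 62% across stages IB to IIB, so events need not be as few as responses.

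**Conclusion.** The concern holds in this form: item 3 pairs an unspecified logistic test with a 0.01 flag in a sample where responders may be very few. Assuming a 20% response rate, the default Wald p-value has a false-positive rate near 0%, far below nominal. It flags markers with correlation 0.5 to 0.8 in about 2% to 10% of trials, against about 23% to 77% for Firth at a false-positive rate near 1%. Wald power is below 1% at a 10% response rate and about 11% to 49% at 40%.

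This rests on three assumptions: the response rate, the bivariate-normal marker model, and the Wald test being used by default. It does not support saying that the flag cannot be reached or that no marker could be found. It bears only on the objective-response part of an exploratory objective.

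**What to change.** In sections 4.2 and 27.1, item 3:

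- Keep objective response as the outcome. State that it will be fitted by Firth penalised logistic regression, with penalised likelihood-ratio p-values and profile penalised-likelihood intervals. An exact Wilcoxon rank-sum comparison of responders with non-responders is an acceptable alternative, in line with the exact and rank tests in items 5 and 9.
- Report the number of responders beside each result, and state that missing the 0.01 flag is not evidence of no association.
- Optionally add, as supportive only, a Spearman correlation of the biomarker with percent change in the RECIST sum from baseline to the pre-surgery CT. Note that it can lose power when size change in non-responders is mostly noise or inflammation, and that it ignores new and non-target lesions.

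The Cox models need no change on this evidence. The cost is SAP wording and standard software, with no new data or visits. The downside is that Firth odds ratios are slightly shrunken and less familiar to clinical readers.

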20.0 SAFETY

All patients who receive at least one dose of pembrolizumab will be considered evaluable for safety parameters. Additionally, any occurrence of a non-SAE or SAE from time of consent forward, up to and including follow-up visits, will be reported as per Adverse Event Reporting sections below. Safety will be evaluated for all treated patients using the National Cancer Institute (NCI) Common Terminology Criteria for Adverse Events (CTCAE), Version 4.0 (<http://ctep.cancer.gov>). Safety assessments will be based on medical review of adverse event reports and the results of vital sign measurements, physical examinations, and clinical laboratory tests.

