From the time of treatment allocation/randomization through 30 days following cessation of treatment, all adverse events must be reported by the investigator. Such events will be recorded at each examination on the Adverse Event case report forms/worksheets. The reporting timeframe for adverse events meeting any serious criteria is described in section 20.5.1 & 20.6. The investigator will make every attempt to follow all subjects with non-serious adverse events for outcome.

Adverse events will not be collected for subjects during the pre-screening period (for determination of archival tissue status) as long as that subject has not undergone any protocol-specified procedure or intervention. If the subject requires a blood draw, fresh tumor biopsy etc., the subject is first required to provide consent to the main study and AEs will be captured according to guidelines for standard AE reporting.

20.3 Definition of an Overdose for This Protocol & Reporting to Sponsor and to Merck

For purposes of this trial, an overdose of pembrolizumab will be defined as any dose of 1,000 mg or greater (≥ 5 times the indicated dose). No specific information is available on the treatment of overdose of pembrolizumab. Appropriate supportive treatment should be provided if clinically indicated. In the event of overdose, the subject should be observed closely for signs of toxicity. Appropriate supportive treatment should be provided if clinically indicated.

If an adverse event(s) is associated with (“results from”) the overdose of a Merck product, the adverse event(s) is reported as a serious adverse event, even if no other seriousness criteria are met.

If a dose of Merck’s product meeting the protocol definition of overdose is taken without any associated clinical symptoms or abnormal laboratory results, the overdose is reported as a non-serious Event of Clinical Interest (ECI), using the terminology “accidental or intentional overdose without adverse effect.”

All reports of overdose with and without an adverse event must be reported within 24 hours to the Duke Sponsor (DCI Safety Desk) who will report within 2 working days to Merck Global Safety. (Attn: Worldwide Product Safety; [contact])

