	Time Course	Did the AE follow in a reasonable temporal sequence from administration of Merck product? Is the time of onset of the AE compatible with a drug-induced effect (applies to trials with investigational medicinal product)?
	Likely Cause	Is the AE not reasonably explained by another etiology such as underlying disease, other drug(s)/vaccine(s), or other host or environmental factors

Relationship to Merck Product (continued)	The following components are to be used to assess the relationship between the test drug and the AE: (continued)	
	Dechallenge	Was Merck product discontinued or dose/exposure/frequency reduced? If yes, did the AE resolve or improve? If yes, this is a positive dechallenge. If no, this is a negative dechallenge. (Note: This criterion is not applicable if: (1) the AE resulted in death or permanent disability; (2) the AE resolved/improved despite continuation of the Sponser's product; or (3) the trial is a single-dose drug trial); or (4) Sponser's product(s) is/are only used one time.)
	Rechallenge	Was the subject re-exposed to Merck product in this study? If yes, did the AE recur or worsen?

		
If yes, this is a positive rechallenge. If no, this is a negative rechallenge. (Note: This criterion is not applicable if: (1) the initial AE resulted in death or permanent disability, or (2) the trial is a single-dose drug trial); or (3) Sponser's product(s) is/are used only one time).
 
NOTE: IF A RECHALLENGE IS PLANNED FOR AN ADVERSE EVENT WHICH WAS SERIOUS AND WHICH MAY HAVE BEEN CAUSED BY MERCK PRODUCT, OR IF REEXPOSURE TO MERCK PRODUCT POSES ADDITIONAL POTENTIAL SIGNIFICANT RISK TO THE SUBJECT, THEN THE RECHALLENGE MUST BE APPROVED IN ADVANCE BY THE SPONSER AS PER DOSE MODIFICATION GUIDELINES IN THE PROTOCOL.

	Consistency with Trial Treatment Profile	Is the clinical/pathological presentation of the AE consistent with previous knowledge regarding Merck product or drug class pharmacology or toxicology?
The assessment of relationship will be reported on the case report forms /worksheets by an investigator who is a qualified physician according to his/her best clinical judgment, including consideration of the above elements.		
Record one of the following	Use the following scale of criteria as guidance (not all criteria must be present to be indicative of Merck product relationship).	

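### The only planned adverse event table is limited to treatment-related events, so no all-cause adverse event summary is planned although every event is collected

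*Combined protocol and SAP*

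**What the plan says.** Item 6 of the secondary objectives in Section 27.1 reads "Treatment-related adverse events will be summarized by type and grade". Section 4.2 carries the same restriction with a slip of wording: "Treatment-related adverse evaluate will be summarized by type and grade". Neither place says to which treatment the events must be related.

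Under adverse event monitoring, Section 27.1 says: "In this trial design it is difficult to accurately attribute adverse events to pembrolizumab, surgery, or other causes". It then sets two criteria for judging pembrolizumab followed by surgery. The first concerns deaths "related to any of the study treatments from the first pembrolizumab treatment until 30 days after surgery exceeds 17" per cent. The second concerns patients "deemed unable to go to surgery due to adverse events attributed to neoadjuvant therapy exceeds 20" per cent.

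Collection is wider than the planned summary. Section 20.0 says "All patients who receive at least one dose of pembrolizumab will be considered evaluable for safety parameters", and Section 20.2 says "From the time of treatment allocation/randomization through 30 days following cessation of treatment, all adverse events must be reported by the investigator". Section 20.8 (Table 6) has the investigator record CTCAE grade, dates and a yes/no relationship for each event. That relationship is to pembrolizumab only. It is guided clinical judgement: the table notes that "not all criteria must be present to be indicative of Merck product relationship".

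**The concern.** The plan applies a filter to its one adverse event table and, in the same section, says the judgement behind that filter is hard to make accurately. Patients in this trial receive pembrolizumab, then surgery, and often chemotherapy or radiation before more pembrolizumab. An event with a plausible competing cause is the kind most likely to be called unrelated, and it would then leave the summary without trace.

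There is no control arm to show the background rate. If the plan is followed as written, the report shows the events that investigators assigned to treatment. It shows neither the total adverse event burden of the regimen nor the number set aside. A reader could not judge how far the safety picture depends on attribution.

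**Working it through.** The plan states no figure on this point, so there is none to reproduce. The check has three steps: which planned outputs describe adverse events, whether the data for a wider table exist, and whether the omission can be sized.

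**1. What is planned**

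| Output | Where | Selected by attribution? | Adverse events by type and grade? |
|---|---|---|---|
| Item 6 | 4.2 and 27.1 | Yes, treatment not named | Yes |
| Criterion 1 | 27.1 | Yes, any study treatment | No; deaths up to 30 days after surgery |
| Criterion 2 | 27.1 | Yes, neoadjuvant therapy | No; failure to reach surgery |
| Surgery feasibility rate | 4.1 and 27.1 | No | No |
| Disease-free and overall survival | 17.6, 17.7 and 27.1 | No | No |
| Blood analytes against adverse events | 1.5 and 5.1.3 | Not stated | No; association only |
| Medical review, expedited reporting, committee monitoring | 20.0, 20.5.1, 20.6, 20.7 and 27.1 | Not limited to related events | No; surveillance, with no table named |

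One output describes adverse events by type and grade, and it is filtered. The two criteria are filtered as well. The unfiltered endpoints do not describe adverse events.

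**2. What is collected**

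The adverse event definition in Section 20.2 does not depend on relatedness. The same section requires all adverse events to be reported through 30 days after treatment ends, and Section 20.8 has grade and relationship to pembrolizumab recorded. An all-cause table with a related column can be built from the existing case report forms.

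The only recorded causality judgement concerns pembrolizumab, so in practice item 6 would be the pembrolizumab-related subset. Under Table 6, one ground for answering no is that another cause explains the event better. If item 6 uses that scale, an event thought to be better explained by surgery, chemotherapy or radiation does not appear.

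**3. Size of the omission**

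Let N be all recorded adverse events and R those judged related. Item 6 shows R and leaves out N − R, a share of (N − R)/N. The documents give neither N nor R. The share could lie anywhere from 0 (all judged related) to 1 (none judged related), and nothing in the documents narrows that range.

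The schedule shows where item 6 would be the only table, because neither criterion reaches beyond 30 days after surgery:

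- Doses: 2 neoadjuvant + 4 adjuvant = 6, and 4/6 = 67% are adjuvant.
- Scheduled adverse event assessments (Appendix A): 4 up to the post-surgery visit, 0 in the standard chemotherapy/radiation column, and 5 from adjuvant cycle 1 to the end-of-study visit. The total is 9, and 5/9 = 56% are adjuvant.

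Both percentages are scheduled maxima. Sections 3.2 and 9.6 make adjuvant pembrolizumab optional, and Section 9.6 takes patients with positive margins or N2 disease off protocol. They describe the schedule and do not measure lost events.

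**The case against.** The strongest reply is that the plan chose this approach for a reason. Right after calling attribution difficult, Section 27.1 argues that toxicities taken one by one are a poor guide to whether the sequence is safe and feasible, and it rests its verdict on the two criteria. Safety oversight is also not confined to related events: serious events and events of clinical interest are reported whatever the cause, and a committee monitors all toxicity patterns. Item 6 is descriptive and does not forbid a further table. All-cause counts without a control arm cannot be assigned to pembrolizumab.

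Much of this stands. It makes the gap one of planned reporting, not of patient protection. It does not explain why the one table that the plan does promise should be filtered. Oversight is not a planned result, and a table that is merely allowed is not planned.

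A reader might infer that no planned safety result is all-cause, since item 6 and both criteria are filtered. The documents do not support that. Section 27.1 treats safety and feasibility together, and its primary endpoint counts a patient who misses surgery for any reason as a failure. Disease-free and overall survival likewise count deaths of any cause. The claim holds only for adverse event summaries.

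**Conclusion.** The point holds and is minor. No all-cause adverse event summary is planned, although the data for one are collected and the plan calls attribution difficult. The primary endpoint and the stopping rules are unaffected.

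The conclusion rests on reading item 6 as it stands and on there being no other adverse event tabulation in the combined document.

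Two stronger readings should be avoided. The 67% and 56% might be taken as the extent of lost safety information, but actual adjuvant exposure is unknown and the share of events judged unrelated cannot be derived. The remark on attribution might also be read as covering the adjuvant phase. It introduces the criteria for pembrolizumab followed by surgery, so applying it after chemotherapy or radiation is an inference. That inference is reasonable, since Section 11.4 warns that events can appear months after the last dose, but the plan does not state it.

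**What to change.** Replace item 6 in Sections 4.2 and 27.1 with:

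> All adverse events, whatever the judged cause, will be summarised by type and maximum grade in all patients who received at least one dose of pembrolizumab, with events judged related to pembrolizumab shown in an additional column.

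If tables by phase are wanted, use fixed windows:

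- **Neoadjuvant and perioperative:** first dose to 30 days after surgery, matching criterion 1, or to 30 days after the last neoadjuvant dose if there is no surgery.
- **Adjuvant:** adjuvant cycle 1 to the end of safety follow-up, in patients with at least one adjuvant dose.

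The first window should not end at the post-surgery visit. That visit falls 2 to 6 weeks after surgery, so the window would vary between patients. Events between the two windows appear in the all-treated table.

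The cost is SAP wording and a few tables, with no new patients, visits or data. The drawbacks should be stated with the results. All-cause counts include effects of surgery, chemotherapy and radiation and cannot be read as caused by pembrolizumab. Events during standard adjuvant therapy are likely to be under-recorded, because Appendix A schedules no adverse event assessment there and Section 9.7 allows that care to be given by the primary oncology team.
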